10.2. Stratification and randomisation

Patients who meet the inclusion and exclusion criteria will be randomised by telephone message in the ABCSG randomisation centre

Tel. no.: [REDACTED] 8
or
[REDACTED]

Randomisation times:
Mon – Thu 8:30 am – 12:00 pm and 1:00 pm – 3:00 pm
Fri 8:30 am – 2:00 pm

using a computer program and in accordance with the adaptive Pocock and Simon (1975) randomisation method. This computer-aided randomisation procedure ensures that the marginal distribution of the characteristics of the stratification criteria is the same in both treatment groups. The randomisation date is recorded. For randomisation, the personal patient data and stratification criteria must be announced.

The patient number received from the randomisation centre consists of two elements:

- A four-digit number for sequential numbering of patients
- A letter code indicating the treatment arm:
 - A: For Arm A, 2 years of therapy with anastrozole (Arimidex®)
 - B: For Arm B, 5 years of therapy with anastrozole (Arimidex®)

Stratification criteria:

The following stratification criteria are used:

1. PT stage:
 - PT1 (≤ 2 cm)
 - PT2 ($> 2-5$ cm)
 - PT3 (> 5 cm)

2. PN stage:
 - No LN metastasis
 - 1-3 LN metastasis
 - 4-9 LN metastasis
 - ≥ 10 LN metastasis

3. Adjuvant primary hormone therapy:
 - 5 years anti-oestrogen
 - 2 years + anti-oestrogen + 3 years anastrozole
 - Comparable endocrine therapy

4. Adjuvant chemotherapy:
 - Anthracycline-containing CT
 - Taxane-containing CT
 - Other CT
 - No CT

5. Study participation:
 - Study 8 from ABCSG
 - Study 9 from ABCSG
 - None

6. Receptor status:
 - ER+PgR+
 - ER+PgR-
 - ER-PgR+

In principle, the result of the examination of the biochemical receptor determination should override that obtained by immunohistochemistry.

7. State:
 - Vienna
 - Lower Austria
 - Burgenland
 - Styria
 - Carinthia
 - Upper Austria
 - Salzburg
 - Tyrol
 - Vorarlberg

10.3. Interim analyses

An interim analysis is carried out once 2/3 of the target recruitment is reached using a significance level of 0.001, according to the guidelines of Geller and Pocock (1987). If an unexpectedly strong therapeutic effect occurs, the study may be discontinued early.

10.4. Efficacy analysis

The final analysis is carried out according to the intent-to-treat principle of all randomised patients who meet the inclusion and exclusion criteria, have at least one follow-up examination after randomisation, and have survived for 2 years relapse free. They will be assigned to the group into which they were randomised regardless of whether they actually received the therapy or which one.

The graphical representation of the therapeutic effect on the primary and secondary target variables (DFS, overall survival and occurrence of secondary cancers, contralateral breast cancer and fractures) is based on the survival functions according to Kaplan and Meier (1958). The differences between the two study arms are tested using the log-rank test (Mantel (1966)).

In addition, the regression model according to Cox (1972) is used in an exploratory way to examine whether the consideration of additional prognostic factors modifies the results of the log-rank tests. This takes into account primarily the stratification criteria of the randomisation but also other prognostic factors. Differences in the therapy are quantified using hazard ratios (relative mortality risk during therapy compared with the control group). In addition, possible interactions of the therapy with other prognostic factors are examined. In the event of significant interactions, subgroup analyses are carried out.

All calculations are performed using the statistical software SAS® (Statistical Analysis Software; version 8) and all tests are two-tailed, where $p \leq 0.05$ is deemed statistically significant.

10.5. Safety analysis

The safety analysis is based on all randomised patients who started the therapy. All serious adverse events, adverse events leading to therapy discontinuation and fracture rates observed during or after therapeutic administration of the study drug are recorded. The worst value per patient is included in the analysis.

[figure not shown]
The laboratory data measured is described and maximum and minimum measurements are presented over time or by maximum deviations from the normal range. In addition, absolute and percentage changes from the baseline measurement values and maximum fluctuations over time are described.

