10. STATISTICAL ANALYSIS

10.1. Sample size

From randomisation, all patients receive the same therapy for 2 years, and one group for a further 3 years. Any difference between the groups is thus only to be expected after 2 years from randomisation. Therefore, 2 years after randomisation (= change of therapy) is defined as the primary time of interest for the analysis for each patient.

It is expected that 700 patients may be recruited per year. Considering that 5% of the patients drop out in the first two years due to relapses, 665 patients per year remains an effective recruitment rate.

A difference between the treatment group and the control group of 0.916 and 0.937 after 3 years from the date of change of therapy in exponential survival (which corresponds to a hazard ratio of 1.35) can be disclosed with a power of 85% and a bilateral significance level of 5% when 433 events are observed. This will be achieved when 665 patients are recruited over 5 years and followed up for a further 2.7 years. This produces a sample size of 3500 patients of which 3325 are evaluable. The expected total duration of the study is 9.7 years. At an exponential drop-out rate of 7%, the power would reduce to 80%.

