### 3.3.3. Safety (SAF) population

Safety analyses will be based on the SAF population and include all enrolled and treated patients. Hence, all patients who were randomized and received at least one dose of study treatment.

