### 3.6.4. Time to first clinical fracture

This is defined as the time from two years after randomization to first clinical fracture. Patients without clinical fractures were censored at their last therapy visit (maximum approximately 5 years after randomization).

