## 3.7. Safety evaluation

Analyses of the safety data are based on the SAF population. Only serious adverse events (SAEs) and adverse events (AEs) leading to discontinuation of the therapy are collected in this trial. Frequencies of serious adverse events will be summarized descriptively per treatment arm and in total. Patient listings of SAEs and of AEs leading to discontinuation of the therapy will be given. Change in tumor markers CEA and CA 15-3 will be descriptively summarized (e.g., means, median, standard deviations, ranges).

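### SAEs are summarised by arm over the whole study with no split at month 24, although the arms differ only after it; with equal reporting, about 45% of the relative excess is lost

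*Protocol*

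**What the plan says.** Protocol 10.1 states the design fact on which this point turns: "From randomisation, all patients receive the same therapy for 2 years, and one group for a further 3 years". It concludes that the arms can diverge only from 2 years after randomisation. SAP 2.4 repeats this. The SAP then starts the main analyses of DFS (3.5.2), overall survival, contralateral breast cancer and secondary carcinoma (3.6.1 to 3.6.3) at 2 years. Fractures follow the same clock in SAP 3.6.4: "This is defined as the time from two years after randomization to first clinical fracture".

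The safety sections do not use this starting point. Protocol 10.5 covers all randomised women who started therapy. It pools SAEs with "adverse events leading to therapy discontinuation and fracture rates observed during or after therapeutic administration of the study drug are recorded", and adds: "The worst value per patient is included in the analysis". The SAP safety population is "all patients who were randomized and received at least one dose of study treatment". For that population SAP 3.7 plans: "Frequencies of serious adverse events will be summarized descriptively per treatment arm and in total". It also plans listings: "Patient listings of SAEs and of AEs leading to discontinuation of the therapy will be given". Neither section mentions a split at month 24, a person-time rate or an adjustment for exposure.

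Two further places decide which SAEs reach the table. Protocol 9.3.2 asks for SAE reports after the drug ends only within 30 days, or later if a causal link cannot be ruled out. Section 7.3 as changed by Amendment 1 gives Arm A visits at 36, 48 and 60 months modelled on the Arm B therapy visits, and those visits include SAEs.

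**The concern.** The safety question in this trial is what 3 more years of anastrozole add. A by-arm SAE table that runs from randomisation mixes that contrast with 2 years of identical treatment. If each woman is counted once, a woman with an SAE in months 0-24 is already in the table. A later SAE in her, in the only period when the arms differ, changes the table only if it is worse and severity is shown. The arms can then look more alike than they are in the period that matters, and this bears on the benefit-risk judgement between 2 and 5 years. The plan applied the 2-year logic to its efficacy endpoints and to fractures, but not to SAEs.

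**Working it through.** The documents state no SAE rate and no figure for dilution, so there is no planned figure to reproduce.

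**Assumptions.** Constant SAE rate λ of 5%, 8% or 12% a year. Arm A stays at λ throughout. Arm B has rate rλ after month 24. SAEs are captured equally in both arms to month 60. Each woman is counted once.

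**Formulas.**
- Risk by month 24, equal in both arms: p2 = 1 - exp(-2λ)
- Whole study: pA = 1 - exp(-5λ); pB = 1 - exp(-2λ - 3rλ)
- Months 24-60: qA = 1 - exp(-3λ); qB = 1 - exp(-3rλ)
- Since pA = p2 + (1 - p2)qA, and likewise for B, pB - pA = (1 - p2)(qB - qA). The share of the absolute excess lost is p2.
- Dividing by pA and qA, the share of (ratio - 1) lost is p2/pA, which does not depend on r.

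**Results for r = 1.20.**

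| λ per year | p2 = absolute excess lost | Whole study, A vs B (ratio) | Months 24-60, A vs B (ratio) | Relative excess lost, p2/pA |
|---|---|---|---|---|
| 5% | 9.5% | 22.1% vs 24.4% (1.10) | 13.9% vs 16.5% (1.18) | 43% |
| 8% | 14.8% | 33.0% vs 36.1% (1.10) | 21.3% vs 25.0% (1.17) | 45% |
| 12% | 21.3% | 45.1% vs 48.9% (1.08) | 30.2% vs 35.1% (1.16) | 47% |

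At 8% a year the absolute excess is 36.1 - 33.0 = 3.1 points over the whole study, against 25.0 - 21.3 = 3.7 points after month 24. With r = 1.5 the ratios are 1.23 and 1.42, and the relative loss is again 45%.

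**Two variations.**
- If Arm A's rate instead falls when the drug stops, 2-year risks of 5-20% and hazard ratios of 1.25-2.0 give a relative loss of 47-62%. The absolute loss is still p2.
- If the table counts events, not women, nothing is masked and no absolute excess is lost. The ratio is still diluted: (2 + 3r)/5 = (2 + 3.6)/5 = 1.12 for a true 1.20, a loss of 2/5 = 40%.

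**What unequal capture would do.** Suppose there is no true effect, λ = 8%, and Arm A's SAEs are captured only to 30 days after the drug ends at 2 years.
- Whole study: Arm A 1 - exp(-0.08 × (2 + 30/365)) = 15.3%; Arm B to month 60 33.0%; ratio about 2.
- Months 24-60: Arm A 1 - exp(-0.08 × 30/365) = 0.7%; Arm B 21.3%; ratio above 30.

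Both excesses are spurious, and the split makes the artefact larger.

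**The case against.** Several stronger readings are tempting, and the documents do not support them.

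- **That half of any excess harm is hidden.** This is near the truth only on the relative scale. On the absolute scale, which matters most for benefit-risk, the loss is the 2-year risk: about 15% at 8% a year.
- **That the table must understate harm in Arm B.** That requires equal SAE capture. If Protocol 9.3.2 governs, Arm A is recorded for about 3 years less and the table would overstate the excess. Amendment 1 points the other way, so the direction cannot be stated flatly.
- **That the analysis rests only on one worst value per woman.** That rule stands in Protocol 10.5. SAP 3.7 does not repeat it and adds patient listings. Under the rule a worse later value replaces an earlier one, and the protocol also describes laboratory data over time ("maximum and minimum measurements are presented over time or by maximum deviations from the normal range").
- **That safety ignores the 2-year point altogether.** Fractures are analysed from 2 years, as are deaths and second cancers, which are also SAE categories under Protocol 9.2.
- **That AEs leading to discontinuation suffer in the same way.** A woman discontinues once, so an early event cannot mask a later one. After month 24 an Arm A woman who followed the plan has no study drug left to stop.

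It is also fair to say that SAP 3.7 is descriptive and plans no test, so loss of power is not the issue. These objections narrow the point to the SAE table. They do not answer why that table alone keeps the undivided clock. Nor do the listings replace a summary by period.

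**Conclusion.** The point holds for the SAE summary. SAP 3.7 and Protocol 10.5 pool 2 years of identical treatment with the 3 years in which the arms differ, against the logic that the plan applies to its main time-to-event analyses. If capture is equal to month 60, the pooled table loses roughly 45% of the relative excess and about 10-21% of the absolute excess. These sizes rest on constant rates of 5-12% a year, assumed here because the documents give none. If capture is unequal, the bias may run the other way. A single pooled table cannot show which of the two is at work. This is a gap in the planned presentation and is inexpensive to close; it does not show that harm will be concealed.

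**What to change.** In SAP 3.7, with matching wording in Protocol 10.5:

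1. Keep the whole-study SAE table.
2. Add SAE tables for randomisation to month 24 and for months 24-60, counting each woman once within each period. In the second period use as denominator the treated women still under observation at month 24, and give person-time rates.
3. Reconcile Protocol 9.3.2 with section 7.3 as amended, and state whether Arm A SAEs in months 24-60 were captured as in Arm B. Use the second-period table for the 2 versus 5 year comparison only if they were. Otherwise label it as not comparable between arms.
4. Use months 0-24, when the planned drug is the same, as a check on differential reporting in this open-label trial.
5. Compare AEs leading to discontinuation between arms for months 0-24 only. After month 24, describe them for Arm B alone.

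The cost is SAP wording, one reconciliation and a split by event date. The downside is more tables with fewer events in each.

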10.6. Substitution of patients

No patient who meets the inclusion and exclusion criteria and who stops taking part in the study early for any reason will be replaced.

11. DATA MANAGEMENT

Data is managed by the ABCSG in cooperation with the contract research organisation CRS Creative Research Solutions GmbH using the IntTrial® system. IntTrial® is a modular system based on the universal PDF format for creating, evaluating and archiving study CRFs. The following diagram provides an overview of the “CRF flow” on IntTrial®:

11.1. Patient identification list

All patient-related data will be recorded in anonymous form. Each patient is assigned a patient number at randomisation that uniquely identifies them by their initials and date of birth. The investigator will keep a confidential patient list, in which the identifying data is linked to the patients’ full name and optionally the insurance number.

11.2. Data collection / documentation sheets

11.2.1. Documentation

At the study sites, all data required by the study protocol as well as objective and subjective information must be entered directly into the relevant medical files/original patient documentation before documentation in the CRF.

All data collected during the study is entered into the designated documentation forms (CRFs) by the investigator or a person who has previously been authorised in writing. These provide a mirror image of the requirements according to the protocol.

If an examination has not been completed, this will be indicated with “n.d.”. If information is not available, this will be documented with “n.a.”.

The IntTrial® system allows the investigator to document study data electronically (“on-screen”; “e-CRF”) or conventionally on a paper CRF. The study CRF is made available on CD-ROM. The CD-ROM contains all CRF pages both in the form of fillable PDF documents (e-CRF) and as a print version, which can be printed out and completed by hand.

After completion on computer, the CRF pages are sent to Data Management by email. Alternatively, the pages can also be printed out and either faxed or sent by mail. A copy of each page sent is kept at the site, either in electronic or paper form.

In the case of conventional documentation, the print template of the CRF is used. Fully completed pages are sent by post or faxed to Data Management. All entries must be made in permanent black or blue ballpoint pen to ensure the legibility of all copies.

It is important that documentation is completed soon after therapy. Documentation should therefore be completed and sent to Data Management within 7 days of a visit.

The completed CRF pages are sent to:

ABCSG Data Management
FAO [REDACTED]
[name]
[name]

Study fax: [REDACTED]

Study email: [REDACTED]

11.2.2. Subsequent corrections to documentation

Once a CRF page has been completed on the computer and forwarded to Data Management, the page can no longer be corrected by the investigator and resubmitted to Data Management. The CRF page is entered into the preliminary database and further adjustments may only be carried out again during SDV.

If a CRF page is accidentally sent to Data Management twice, the second page will not be input, but simply archived. SDV is performed on the first version of the respective CRF page.

The same rules apply to paper CRFs. Since in this case, entries are made by hand, corrections made during documentation are made in accordance with the usual rules. An incorrect entry is crossed out, however, the deleted entry must remain recognisable. The corrected value should be written next to it. The date of the change and signature/initials of the investigator or authorised person must be added to each correction. The use of correction fluid is prohibited.

11.3. Data acquisition

Data acquisition is carried out by the person responsible for data management. Data entry takes place on an ongoing basis, in parallel with the clinical trial.

11.3.1. Data entry / obvious corrections / queries

CRFs received by Data Management are included in the preliminary study database. A system consisting of the Cardiff Teleform Reader, the Teleform Verifier and MS-SQL is used for the input process with IntTrial®. The input process is divided into automatic data acquisition, followed by a manual check by the data entry staff, with each value being checked subsequently.

A copy of each CRF page is automatically archived in electronic format as an indexed PDF. Corrections of obvious mistakes in the documentation (obvious corrections) are made immediately during input by the input staff and the changes are logged in the database. Missing, contradictory or illegible entries are also logged as queries in the database.

11.3.2. Creating an electronic copy of the CRF for source data verification (SDV)

To enable the study data to be monitored, the data from each CRF page included in the preliminary study database is exported into a blank CRF form. The obvious corrections made as well as the queries logged in the database are exported into the form.

These CRF pages are then made available to the competent monitor for source data adjustment. During SDV, queries already listed are processed and the CRF page is signed by the investigator after any corrections are made. A copy of the signed CRF remains at the site and the original is given to the monitor.

11.3.3. Data entry / database validation / database lock

The signed CRF pages are forwarded by the monitor to Data Management and then entered into the database again from there. This data is then validated by a final query process, based on checks for validity, consistency and plausibility.

Query forms to clarify any queries are passed on to the investigator for processing via the monitor. After processing, these are sent back to Data Management, and a copy is retained at the site.

After clarification of all possible queries using query forms, the database is closed. The analysis and statistical analysis is carried out using SAS[®] (Statistical Analysis Software) version 8.

11.4. Original data in the CRF

All data collected within this protocol must be available as original data in the respective medical history. Direct entries in the CRF are not considered to be source data.

11.5. Storage of CRFs

Once the study is completed, the documentation remains with the ABCSG. The originals of all central study documents including the documentation sheets are stored at the study site for at least 15 years after the end of the study. CRFs can also be stored on image carriers or other data storage devices.

During the study, one copy of the CRF remains with the respective investigator. The investigator also retains the administrative documents produced (correspondence with the Ethics Committee, BUMI, AstraZeneca, study site etc.), the patient identification list, signed informed consent forms, copies of documentation sheets and the general study documentation (protocol, amendments) for the period of time stated above.

Original data on study patients (medical files) must be stored in accordance with the archiving term applicable to the study sites, however, for a minimum of 15 years.

If the investigator does not stay at the study site for whatever reason (e.g. retirement, appointment elsewhere), the retention of the documents must be handed over to a successor, who consequently takes on the responsibility, and this must be documented in writing. Both AstraZeneca and the ABCSG must be informed of such a transfer in writing.

12. LEGAL AND ETHICAL PRINCIPLES

12.1. Legal basis

The study complies with

- The Declaration of Helsinki (1996 version, Appendix A)
- The currently valid Austrian AMG Section 2a and III. Sections 28 to 48
- and GCP/ICH.

12.2. Ethics Committee

Prior to commencement of the study, the vote from the competent Ethics Committee is obtained by the STS of ABCSG. This is the responsibility of the employee for Regulatory Affairs at the ABCSG.

Once the investigator receives the written vote, a copy is forwarded to AstraZeneca and the ABCSG-STs.

The Ethics Committee must also be informed by the ABCSG-STs of serious adverse events at the site, changes to the protocol (Amendments) as well as the discontinuation of the study.

12.3. Patient data and data protection

The investigator will not pass on the patient's name or other personal information. The collected patient data will be used only in anonymous form for the purposes of scientific work, and where necessary, for submission to the regulatory authorities by AstraZeneca. If it is necessary to identify the name of the patient during the course of the study for medical reasons, this will be done while maintaining the confidentiality of the persons involved in the study. The investigator keeps a separate Patient Identification List, which enables the randomisation numbers to be allocated to the names and addresses of the patients at any time. These Patient Identification Lists are stored in the IF.

Medical files can be viewed by authorised persons as part of monitoring, an audit by AstraZeneca or inspection by the authorities. The patient declared her written consent to this prior to the start of the trial.

The relevant provisions of the data protection legislation will be fulfilled.

